In this study, lower limb stiffness and gait mechanics will be evaluated in healthy, able-bodied adult participants across three conditions; "NoBrace" where participants are asked to walk normally with no bracing, "Stiff" where participants are asked to walk while wearing a Malleo-Lok with stiff struts, "Compliant" where participants are asked to walk while wearing a Malleo-Lok with compliant struts. Testing will occur in a randomized order. Questionnaires will be used to quantify participants' pain and perceived comfort and smoothness during walking. A motion capture system will be used to evaluate walking biomechanics and overall ankle joint level stiffness, allowing for comparisons between conditions. Small reflective markers will be placed on the participant's skin and lower limb forces, and body motion will be assessed using computerized motion capture cameras and force plates in the floor. Muscle activity data will be collected using non-invasive wireless surface electromyography sensors.

Objectives and Specific Aims:

Aim 1: Determine the effect of Malleo-Lok stiffness on lower limb mechanics during gait.

Hypothesis 1.1: We hypothesize that increasing stiffness of the Malleo-Lok will result in decreased ankle range of motion and increased knee flexion during gait.

Hypothesis 1.2: We hypothesize that increasing Malleo-Lok stiffness will result in an earlier, faster center of pressure progression

Aim 2: Determine the effect of Malleo-Lok stiffness on overall joint level stiffness.

Hypothesis 2.1: We hypothesize that measured stiffness will progressively increase between the NoBrace, Compliant and Stiff conditions.

Aim 3. Determine the within-session reliability of a novel in-vivo weight bearing approach to evaluating AFO

stiffness.

Hypothesis 3.1: We expect the novel approach to demonstrate excellent within-session reliability.

Background and Significance:

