A1) Ankle foot orthoses (AFOs) are medical devices often used to support the foot and ankle during daily activities. AFO device stiffness can influence the level of support provided and motion at the ankle. There is a general consensus that increasing AFO stiffness decreases overall ankle range of motion[1-3] noticeably reducing peak ankle dorsiflexion[1,2,4-7] and plantarflexion.[1,8] In addition to effects at the ankle, AFO stiffness has been found to affect the knee during gait, with increased stiffness generally resulting in increased knee flexion at initial contact[1] increased peak knee flexion during stance phase[1,3,8,9] and decreased peak knee extension.[1,4] However, previous studies have focused on traditional posterior strut devices with the strut aligned in the frontal plane to allow sagittal plane deflection. The effect of lower profile devices with laterally positioned struts are poorly understood. In this study we will determine if the Malleo-Lok, a novel carbon fiber brace utilizing lateral struts, produces similar effects, and determine the effect of device stiffness.

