Each participant will be given time to accommodate to the brace prior to collection. Participants will then undergo testing in each study condition (Stiff, Compliant, NoBrace) to determine how orthosis stiffness affects gait biomechanics and overall joint stiffness. We will use well-established techniques to obtain a range of biomechanical data as individuals walk at self-selected and controlled speeds.

Personal/demographic and anthropometric information will be used to fully characterize the study participants. Demographic factors include characteristics that are independent of the health condition but can potentially influence physical performance and an individual's course of recovery. We will collect multiple variables that have been previously associated with outcomes, including race, ethnicity, and education to characterize the cohort. Anthropometric and demographic information, such as age, biological sex, height, weight, leg length, shoe type, shoe length and width will also be used to characterize the cohort.

Patient-reported outcomes questionnaires will be used to evaluate participant pain, comfort and smoothness. These patient-centric assessments will provide insight that can be used to interpret other study findings. We have used the selected measures in the target population and expect that they will effectively capture device-related outcomes.

Comfort and smoothness will be assessed using a modified version of the Socket Comfort Score, a reliable, valid, and sensitive measure of device fit and comfort.[23] These measures have been shown to effectively capture patient perception, are responsive to simple modifications to CDO device function, and will be applied in a manner consistent with a prior publication by the research team.[24] Comfort scores range from 0 = most

uncomfortable to 10 = most comfortable, and from 0 = least smooth to 10 = most smooth.[23]

Pain will be assessed using a standard 11-point numerical pain rating scale, in which 0 = no pain and 10 = worst pain imaginable, in a manner consistent with multiple other protocols.[25,26] Using this highly reliable approach, participants will be asked to rate their pain at the start of each session, and report their pain with movement in the device (if any) during each walking condition.

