Video recordings will be collected during walking trials. Recordings will include walking on the level over ground surface in each condition and at each walking speed. The camera will be positioned so the top of the field of view will be at the shoulders to minimize the likelihood of capturing the participants face, and the files will be stored securely as described in section X.4 and will only be available to members of the research team. Collection of video recordings is required during testing for quality control purposes. Video recordings will be removed from the video camera after being transferred to the secure network drive server and will be retained to facilitate future analysis consistent with "Data Storage for Future Use" section in the informed consent document.

Statistical Analysis Plan:

Analysis Methods:

There is one independent variable (IV) in this study, stiffness of the ankle brace (compliant and stiff). All the primary dependent variables (e.g. ankle moments, ankle range of motion, push-off power, ankle joint stiffness) will be evaluated using similar statistical approaches within each group. One-way repeated measure ANOVAs will be used to evaluate the effect of brace stiffness. Paired t-tests with Bonferroni-Holm correction will be used for post-hoc comparisons. Multiple trials will be collected for each condition during in-vivo ankle-CDO stiffness testing. Intraclass correlation coefficients and minimal detectable changes values will be calculated for in-vivo ankle-CDO stiffness between the average measurement for time point 1 and time point 2.

Power Analysis:

The number of participants proposed for this study are consistent with those from prior investigations by [name] related to AFO design. Thirteen participants was sufficient to detect differences associated with AFO stiffness in a recent study by [name] (PMID: 25193884). A total of 20 participants were included to adequately evaluate reliability in Aim 3.

Literature Cited:

21. Wilken, J.M., et al., Reliability and Minimal Detectable Change values for gait kinematics and kinetics in healthy adults. *Gait Posture*, 2012. 35(2): p. 301-7.
22. Kaufman, K., et al., Reliability of 3D gait data across multiple laboratories. *Gait Posture*, 2016. 49: p. 375-381.
23. Hanspal, R.S., K. Fisher, and R. Nieveen, Prosthetic socket fit comfort score. *Disabil Rehabil*, 2003. 25(22): p. 1278-80.

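### Does the open list of primary variables in the SAP leave the main results to be chosen after the data are seen?

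*Combined protocol and SAP*

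**What the plan says.** - **Ranking of outcomes.** Only the Statistical Analysis Plan (Analysis Methods) ranks outcomes, and it does so by example: "All the primary dependent variables (e.g. ankle moments, ankle range of motion, push-off power, ankle joint stiffness". All of them are to be handled in a similar way: a one-way repeated-measures ANOVA, then paired t-tests with Bonferroni-Holm correction. No alpha is stated and the Holm family is not spelled out.
- **Aims and hypotheses** (Objectives and Specific Aims). Aim 1 is broad: "Determine the effect of Malleo-Lok stiffness on lower limb mechanics during gait". Hypothesis 1.1 expects that "increasing stiffness of the Malleo-Lok will result in decreased ankle range of motion and increased knee flexion during gait". Hypothesis 1.2 expects that "increasing Malleo-Lok stiffness will result in an earlier, faster center of pressure progression". Hypothesis 2.1 expects that "measured stiffness will progressively increase between the NoBrace, Compliant and Stiff conditions".
- **Measures** (Design and Methods). Joint moments and power are among the quantities to be computed. Centre of pressure is given two explicit measures, peak velocity and time to that peak. No knee measure is specified.
- **Conditions, speeds and postures** (Design and Methods). Participants undergo "testing in each study condition (Stiff, Compliant, NoBrace"), and gait data are taken "as individuals walk at self-selected and controlled speeds". Stiffness is tested both standing and sitting. Neither speed and neither posture is called primary.

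**The concern.** The list of primary variables and the hypotheses do not line up, and the list is open-ended. Two hypothesised outcomes are missing from it, and two of its entries have no hypothesis. Knee flexion could be read in several ways: Background and Significance (A1) describes earlier findings as "increased knee flexion at initial contact[1] increased peak knee flexion during stance phase[1,3,8,9] and decreased peak knee extension", which is three different measures. Combined with two speeds, that suggests six ways to claim support for the knee part of Hypothesis 1.1, with no correction between them. If the best-looking route were reported as the planned one, a reader could not tell, and the error rate attached to the claim would be higher than it appears. The contrast most exposed is Stiff against Compliant, which is central to a study of brace stiffness.

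**Working it through.** **1. The lists side by side.**

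| Outcome | Hypothesis | Named in the SAP list | Measure fixed |
|---|---|---|---|
| Ankle range of motion | 1.1 | yes | yes |
| Knee flexion | 1.1 | no | no |
| Centre-of-pressure speed and timing | 1.2 | no | yes (Design and Methods) |
| Ankle joint stiffness | 2.1 | yes | yes, posture open |
| Ankle moments, push-off power | none (within Aim 1) | yes | in general terms |

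So every hypothesised construct, with its direction, is written down before data. What is open is one knee definition, the speed and the posture. On posture, Aim 3 calls the method weight bearing, and Background (A2) faults an earlier device for leaving out vertical load. Both point towards standing, though neither designates it.

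**2. The plan's own figure.** The Power Analysis cites 13 participants by precedent and 20 for reliability. It gives no alpha, effect size, SD, power or target ICC, so the 20 cannot be reproduced. It is used below only as n.

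**3. The alarming count.** The four named variables at one speed and one posture give 4 ANOVAs. Both speeds for three gait variables and both postures for stiffness give 3×2 + 1×2 = 8. Adding three knee and two centre-of-pressure measures at both speeds gives 8 + 3×2 + 2×2 = 18. At an assumed 0.05 each, if all are null and independent:
- 1 − 0.95^4 = 18.5%
- 1 − 0.95^8 = 33.7%
- 1 − 0.95^18 = 60.3%

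At correlation 0.8, simulation gives about 11%, 16% and 23%. These are chances that something, somewhere, is falsely significant. They describe the study's conclusion only if any one positive result would count as success for the whole study, and the plan does not say that.

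**4. The narrower question: six assumed knee routes.** Simulation with n = 20, three conditions, SD of each paired difference 1, ANOVA at 0.05 then Holm over three pairs, Stiff = Compliant, 20,000 runs (Monte Carlo SE at most 0.003). Chance of at least one false Stiff-Compliant claim:

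| NoBrace shift | One route | Six, corr. 0.9 | Six, corr. 0.8 | Six, corr. 0 |
|---|---|---|---|---|
| 0 | 0.014 | 0.036 | 0.049 | 0.081 |
| 0.5 SD | 0.025 | 0.063 | 0.084 | 0.150 |
| 1.0 SD | 0.045 | 0.103 | 0.139 | 0.251 |
| 1.5 SD | 0.051 | 0.117 | 0.144 | 0.264 |

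Check: six independent single tests give 1 − 0.95^6 = 0.265, against 0.264 in the last cell.

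Hypothesis 1.1 is directional. At 1.0 SD the false claims in the hypothesised direction are 0.052 (correlation 0.9) and 0.070 (0.8). The like-for-like single route is about half of 0.045, or 0.023.

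The 25% figure needs zero correlation between measures of the same knee in the same people, plus a 1 SD NoBrace effect on every route.

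**5. What analysing everything gives.** The one-route column is the error of each variable taken on its own: 1.4% to 5.1%, so at or below 5% within simulation error.

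**6. Two levels or three.** The SAP gives the independent variable as compliant and stiff only, while Design and Methods has three conditions. Hypothesis 2.1 needs NoBrace, and a Holm-corrected set of post-hoc tests has a purpose only with three levels, so this reads as a clerical slip. With two levels one route would be 5%, and six routes about 11% (correlation 0.9) to 26.5% (correlation 0).

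**7. The price of stricter rules** (noncentral t for the paired test, 80% power, n = 20).
- Five Stiff-Compliant contrasts under Holm across variables: smallest threshold 0.05/5 = 0.01. The detectable effect rises from 0.66 to 0.84 SD, power at 0.66 SD falls from 80% to 55%, and 31 participants would restore it.
- All 15 pairs: 0.05/15 = 0.0033, 0.95 SD, 38% power.
- Requiring both adjacent contrasts for Hypothesis 2.1, with equal steps of 0.66 SD: 60% power, against 78% for Stiff-Compliant alone.

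**The case for a change.** The best case for a change is that it would be cheap. A closed list, one knee definition and a named speed and posture need only wording, ask for no smaller alpha, and would let readers separate planned from chosen results. The hypotheses give constructs, not measures, and the SAP list does not follow them. Nothing ties Hypothesis 2.1 to either posture. Design and Methods also allows that not every activity will be completed, so the data available may vary. A NoBrace effect is plausible from the background, and once the NoBrace pairs are rejected Holm gives the Stiff-Compliant pair little protection.

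Much of this stands as description. The list is open, the knee measure is undefined, and selective reporting is possible. What does not stand is that nothing constrains the choice, or that the plan leads to a wrong analysis. The six routes are built from a literature summary, not from a list of candidate outcomes, and one of the three measures there is peak extension. The same section says the study will see whether this device produces similar effects, which can as well mean reporting all three. The rest of the remedy is preference: demoting moments and push-off power overrides a ranking the sponsor made within Aim 1, choosing one speed and posture discards planned information, and a two-contrast rule costs power.

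**Conclusion.** This is missing detail, not a flaw in the analysis, and no change to the plan is needed. Carried out as written, with every primary variable analysed in the same way and reported whatever its result, the plan gives sound per-variable inference. Analysts can fill the gaps from the document: the hypotheses supply the outcomes, Design and Methods the centre-of-pressure measures and the three conditions, and both speeds and both postures can be shown.

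The risk that remains is selective reporting, which the documents permit but do not show. For the knee outcome its plausible size is 4-5%, 6-8% and 10-14% at NoBrace shifts of 0, 0.5 and 1.0 SD, with about half in the hypothesised direction. That rests on assumptions the documents do not supply: alpha 0.05, Holm over three pairs within each variable, six routes and correlation of 0.8 to 0.9. At zero correlation the figures are 8%, 15% and 25%. Control of error across variables is a fair choice either way in a one-visit study of healthy adults, and with 20 participants it would cost appreciable power.

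### The SAP gives its one factor two levels while the design and Hypothesis 2.1 use three conditions, and it does not say which comparison decides each hypothesis

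*Combined protocol and SAP*

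**What the plan says.** The SAP, under Analysis Methods, defines the factor: "There is one independent variable (IV) in this study, stiffness of the ankle brace (compliant and stiff". It then assigns the test, "One-way repeated measure ANOVAs will be used to evaluate the effect of brace stiffness", and the follow-up, "Paired t-tests with Bonferroni-Holm correction will be used for post-hoc comparisons". It does not say whether NoBrace enters the ANOVA, does not list the post-hoc pairs, and does not tie any hypothesis to a comparison.

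The protocol has three conditions. Purpose and Procedures introduces Stiff, Compliant and a NoBrace condition "where participants are asked to walk normally with no bracing". Design and Methods repeats all three: "Participants will then undergo testing in each study condition (Stiff, Compliant, NoBrace) to determine how orthosis stiffness affects gait biomechanics and overall joint stiffness".

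The hypotheses under Objectives and Specific Aims differ in what they compare:
- Hypothesis 1.1: "increasing stiffness of the Malleo-Lok will result in decreased ankle range of motion and increased knee flexion during gait".
- Hypothesis 1.2: "increasing Malleo-Lok stiffness will result in an earlier, faster center of pressure progression".
- Hypothesis 2.1: "measured stiffness will progressively increase between the NoBrace, Compliant and Stiff conditions".

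**The concern.** The factor in the SAP does not match the design, and each way of resolving the mismatch leaves something open. With two levels, one of the three conditions drops out of the analysis, along with the hypothesis that depends on it. With three levels, the test named for brace stiffness also responds to the presence of a brace.

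The study's primary purpose is to learn whether the stiffness of this device matters. If a reader or author takes a significant three-level F as the answer, a difference caused only by wearing a brace could be reported as a stiffness effect, or as support for a progressive increase across the three conditions.

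**Working it through.** **Inputs.** From the documents: 20 participants (SAP, Power Analysis), three within-subject conditions, one-way repeated-measures ANOVA, paired t-tests with Holm. The documents give no significance level, SD or effect size for these outcomes, so no figure of the plan's own can be reproduced. Assumed: two-sided 0.05, normal errors, sphericity, and effects in units of the SD of a paired difference (that SD set to 1, so the error variance per condition is 0.5).

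**Two-level reading.** With two repeated measures, F = t² on 1 and n − 1 degrees of freedom. A numerical check gave F = 0.01826 and p = 0.894 by both routes. The ANOVA is therefore the Stiff-versus-Compliant paired t-test. There is no further pair for a post-hoc test, and no analysis contains NoBrace.

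**Three-level reading, Stiff equal to Compliant.** Let bracing shift both braces by D. The condition means are 0, D, D, and their squared deviations from the grand mean sum to (2/3)D². The noncentrality of F is

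λ = n × (2/3)D² / 0.5 = 20 × (4/3)D² = 26.67 D²,

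on 2 and 38 degrees of freedom. At D = 0.5, λ = 6.67; at D = 1.0, λ = 26.67. Power from the noncentral F, which agrees with simulation, is in the second column. The other columns are simulated, with the ANOVA followed by Holm over the three pairs.

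| Bracing effect D | Omnibus F significant | Stiff vs Compliant declared | Both Hypothesis 2.1 steps declared |
|---|---|---|---|
| 0.3 | 25% | 2.0% | 0.1% |
| 0.5 | 60% | 2.6% | 0.3-0.4% |
| 0.66 | 84% | 3.2-3.3% | 0.9% |
| 1.0 | 99.6% | 4.7-4.8% | 2.2-2.3% |

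The second column is how often F is significant when stiffness has no effect. The last two are the false claims that remain once the paired tests decide.

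**Without sphericity.** If NoBrace carries extra independent variation with an SD of 1.0, the omnibus rate falls from 84% to 58% at D = 0.66 and from 99.6% to 90% at D = 1.0. The pattern remains, at lower rates.

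**A true progressive increase.** With equal steps of 0.36, the means are 0, 0.36 and 0.72, and λ = 20 × 2 × 0.36² / 0.5 = 10.37, so F is significant in about 80% of studies. Stiff versus Compliant passes Holm in 23-24%, and both steps of Hypothesis 2.1 pass in about 5%. These two figures are practically the same whether or not a significant ANOVA is required first. Steps of about 0.77 are needed for 80% power on both.

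**The case against.** A reader might infer that the plan contains no test of brace stiffness, or that it carries a false-positive rate of 60% to 99.6% for stiffness. The documents support neither.

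- Under the SAP's literal two-level definition, the ANOVA is exactly the Stiff-versus-Compliant comparison that Hypotheses 1.1 and 1.2 need on their plain wording. Only NoBrace and Hypothesis 2.1 are left without an analysis.
- Under the three-level reading, the sentence after the ANOVA supplies Holm-adjusted paired tests. Taken over all pairs, they include Stiff versus Compliant and Compliant versus NoBrace, and they hold the false Stiff-versus-Compliant rate at 2-5%. The SAP nowhere says that F alone settles a hypothesis, so the high omnibus rates are not the error rate of the full procedure.
- Nor is Hypothesis 2.1 made harder by the fix in the sense of falling from 80% to 5% at steps of 0.36. The 80% belongs to a decision on F alone, which the SAP does not state. The ANOVA followed by Holm already gives about 5%.
- Design and Methods lists NoBrace among the conditions used to learn how orthosis stiffness affects gait. The sponsor may therefore regard NoBrace as the lowest stiffness level. The wording of Hypotheses 1.1 and 1.2, which refer to the stiffness of the device itself, points the other way, and the documents do not settle it.

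All of this stands, and it narrows the point. It does not remove the contradiction between two levels and three conditions, or the absence of a stated deciding contrast.

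**Conclusion.** The concern holds as a defect of definition. The factor is misdescribed, and no hypothesis is tied to a comparison. Taken literally, the SAP cannot answer Hypothesis 2.1, and its post-hoc tests have no purpose. Taken with three levels, which the presence of post-hoc tests makes likelier, F by itself shows neither a stiffness effect nor an ordering. The tests that do show these are already planned but are not named as decisive.

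The sizes are illustrative. They rest on the assumed level, normality and an SD-scaled effect, and the omnibus rates also on sphericity. The mismatch between the SAP and the protocol rests on no assumption.

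**What to change.** In the SAP, under Analysis Methods:

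1. Define the factor as condition with three levels: NoBrace, Compliant, Stiff.
2. State that the ANOVA is an overall test and does not by itself decide a hypothesis.
3. Keep the paired t-tests with Holm over the three pairs within each outcome, and list the pairs.
4. Decide Hypotheses 1.1 and 1.2 on the Holm-adjusted Stiff minus Compliant contrast, in the hypothesised direction for each outcome named.
5. Decide Hypothesis 2.1 on Compliant minus NoBrace and Stiff minus Compliant, both significant and positive.
6. Say whether NoBrace counts as the lowest stiffness level in Hypotheses 1.1 and 1.2. If it does, apply the two-step rule there too, with the sign that each hypothesis states.

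The cost is SAP wording only, with no extra data. Hypothesis 2.1 becomes harder to support than on a reading of F alone, but no harder than under the ANOVA-plus-Holm procedure already planned. If the analysis has already been done, the same rules can govern the report, labelled as specified afterwards.

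### Bonferroni-Holm is valid but stricter than needed for three pairwise comparisons: Shaffer's step-down keeps the same 5% family-wise limit and gains 0 to about 8-9 points of power per contrast

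*Combined protocol and SAP*

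**What the plan says.** The Analysis Methods section of the Statistical Analysis Plan sets out two stages. First, "One-way repeated measure ANOVAs will be used to evaluate the effect of brace stiffness". Then, "Paired t-tests with Bonferroni-Holm correction will be used for post-hoc comparisons". It states no alpha. It does not say whether the paired tests depend on a significant ANOVA, or which comparisons form the family that Holm corrects.

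Design and Methods gives three within-person conditions: "Participants will then undergo testing in each study condition (Stiff, Compliant, NoBrace". Hypothesis 2.1, under Objectives and Specific Aims, expects an ordered response: "measured stiffness will progressively increase between the NoBrace, Compliant and Stiff conditions". The SAP, however, introduces the factor with two levels: "There is one independent variable (IV) in this study, stiffness of the ankle brace (compliant and stiff".

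The Power Analysis section gives no effect size, SD or power target. It relies on precedent ("Thirteen participants was sufficient to detect differences associated with AFO stiffness in a recent study") and on the reliability aim ("A total of 20 participants were included to adequately evaluate reliability in Aim 3").

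**The concern.** Holm's procedure suits any set of hypotheses, including unrelated ones. Three pairwise equalities among three means are related, because the NoBrace-Stiff difference is the sum of the two adjacent differences. Once one pair is known to differ, at most one true null remains, and one remaining true null needs no further division of alpha. Holm still halves it at the second step.

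The second step matters for the hypothesis as stated. If means rise in order, the extreme pair (NoBrace-Stiff) usually has the smallest p-value and passes the first step. The adjacent pairs, which show whether the increase is progressive, then meet alpha/2. With 20 participants, a number not derived from pairwise power, some power on those contrasts may be given up for protection beyond the 5% limit.

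**Working it through.** **Inputs.** From the documents: three conditions, so 3 x 2 / 2 = 3 pairs; 20 participants, each tested in every condition; ANOVA, then Holm-corrected paired t-tests. Assumed, because the documents do not give them: two-sided alpha 0.05, normal data, effect sizes and correlations. The SAP states no power figure for these tests, so there is none to reproduce.

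**Thresholds for the ordered p-values**

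| Step | Holm | Shaffer, three means |
|---|---|---|
| 1 | 0.05/3 = 0.0167 | 0.05/3 = 0.0167 |
| 2 | 0.05/2 = 0.025 | 0.05 |
| 3 | 0.05 | 0.05 |

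No Shaffer threshold is below Holm's, so Shaffer can never reject less. Example: for p-values 0.010, 0.030 and 0.200, both reject the first. Holm stops at the second (0.030 > 0.025), whereas Shaffer rejects it (0.030 < 0.05). Neither rejects the third.

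**Why the 5% limit holds.** Two true equalities imply the third, so the number of true nulls is three, one or none.
- Three true: a false rejection needs the smallest p-value to be at most alpha/3. By Bonferroni the probability is at most 3 x alpha/3 = alpha.
- One true: a false rejection needs that one p-value to be at most alpha, which has probability at most alpha.
- None true: no false rejection is possible.

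The argument needs no ANOVA gate and no sphericity assumption.

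**Power, first set-up.** n = 20, SD 1, correlations 0.7 (NoBrace-Compliant), 0.7 (NoBrace-Stiff) and 0.8 (Compliant-Stiff), Greenhouse-Geisser ANOVA gate, 60,000 simulated trials per scenario.

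| Scenario | Contrast | Holm | Shaffer | Gain (points) |
|---|---|---|---|---|
| Steps of 0.25 SD | NoBrace-Compliant | 19.9% | 25.9% | 6.0 |
| | Compliant-Stiff | 26.6% | 32.8% | 6.2 |
| Steps of 0.35 SD | NoBrace-Compliant | 41.7% | 47.6% | 5.9 |
| | Compliant-Stiff | 56.3% | 63.1% | 6.8 |
| Only Stiff differs, 0.5 SD | NoBrace-Stiff | 66.1% | 73.8% | 7.7 |

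At steps of 0.5 SD the gain is about 1 point, at 0.6 SD about 0.2 or less, and at 1 SD nil. Repeat simulations agreed within about 0.6 points. The gate matters little: without it, the last row is 66.3% to 74.4%.

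**Power, second set-up.** n = 20, equal variances, no gate, equal steps expressed as dz (mean paired difference divided by its SD). Power for each adjacent contrast:

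| dz per step | Holm | Shaffer | Gain (points) |
|---|---|---|---|
| 0.40 | 30.0% | 38.0% | 8.0 |
| 0.50 | 49% | 56% | 7 |
| 0.60 | 68% | 72% | 4 |
| 0.80 or more | | | under 0.5 |

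The largest gain over all equal-variance mean patterns searched at n = 20 was 8.9 points.

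**Realised family-wise error.** When all three means are equal, the two methods share their first step and so their error: 4.5% each without the gate, 3.4% each with it (n = 20, equal variances). When only Stiff differs, by 0.5 SD in the first set-up, the one true null (NoBrace = Compliant) is falsely rejected in 3.6% of trials with Holm and 5.0% with Shaffer. Repeat simulation gave 3.4% and 4.7%. At 0.35 SD the figures are 2.6% and 4.3%.

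**The case against.** The strongest objection is that nothing here is wrong. Holm is pre-specified, standard and controls family-wise error strongly. That stands: a reader might infer that the SAP's correction is faulty or its error control deficient, and the documents support neither.

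Second, the gain may be negligible. The only hint of effect size is the precedent of thirteen participants. If that meant 80% power at two-sided 0.05, dz would be about 0.85. At n = 20 with both steps that large, Holm gives 94.7-95.0% and Shaffer 94.8-95.1%. If it meant 50% power (dz about 0.59), the gain is about 3-4 points. The documents do not say which power applied. This stands as a limit on size. It is tempting to say that knee and centre-of-pressure effects will be moderate and so will bear the loss, but nothing in the documents establishes that. In several scenarios where the gain is largest, power is also low under either method.

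Third, the change is not free of any trade. Only the 5% ceiling is the same; Holm's realised error is lower when one null is true. This stands, although the margin is protection beyond the stated limit.

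Fourth, the SAP leaves the Holm family undefined, lists several primary variables, and the protocol has two walking speeds. If Holm was meant to span outcomes or speeds, Shaffer's three-mean thresholds would not carry over. This stands and determines how the fix is worded.

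Finally, one could go further and use unadjusted paired tests after a significant ANOVA, which gained up to 11.3 points in the same search. The SAP does not support that step: it states no gate and no sphericity correction. Ungated unadjusted tests gave 12.4% family-wise error. Gating by an uncorrected F gave 5.7% to 6.4% under the complete null with strongly unequal variances (about 5.1% with Greenhouse-Geisser).

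**Conclusion.** The point holds as an efficiency improvement, not as a defect. For the three comparisons among NoBrace, Compliant and Stiff within one outcome and one speed, Shaffer's step-down is uniformly at least as powerful as Holm and strictly more powerful for some effects, under the same family-wise limit. That follows from the logic of three means and needs no assumption about effect size.

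The size does need assumptions. The figure of 0 to about 8-9 points rests on two-sided alpha 0.05, n = 20 and the assumed effects, variances and correlations. No claim that the trial is underpowered because of Holm can be drawn from the documents. Nor does the two-level wording of the factor show that NoBrace was meant to be left out of the tests. Read literally it would leave a single comparison with nothing to correct, which conflicts with the planned correction and with the three conditions in the protocol.

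**What to change.** In Analysis Methods, replace the Bonferroni-Holm correction with: *Shaffer's step-down correction (ordered p-values compared with alpha/3, alpha, alpha) applied to the three pairwise comparisons of NoBrace, Compliant and Stiff, separately for each outcome and walking speed*. In the same section, give the independent variable three levels (NoBrace, Compliant, Stiff), and state alpha and sidedness.

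The cost is a few words in the SAP and a change of p-value multipliers from 3, 2, 1 to 3, 1, 1. No extra data or ANOVA gate is needed. The downsides are a method less familiar to readers and a realised error closer to 5%. If the sponsor intends one correction across outcomes or speeds, this replacement should not be used as it stands, and that wider family should be defined first.
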